Primary Hypothesis 5: Clients in the experimental condition will have greater cost effectiveness than clients in the control condition. Costs of services provided to the participating clients in the experimental and control conditions during the study time period was estimated in the following way. Services received by each client as documented during the chart review process for Hypothesis 1 above. The cost of each service was estimated using the CPT code for that service (e.g., group psychotherapy = 90853). To establish consistent costs, estimates of cost for each CPT code were derived from Medicare reimbursement estimates in Massachusetts using online tools (e.g., https://www.findacode.com). While not precise, use of Medicare reimbursement is often used to get a general and relative sense of service costs across states. This is especially useful for comparing groups (e.g., experimental versus control), rather than attempting to generate precise cost estimates. Costs per individual were summed and averaged for t-test comparison between experimental and control groups. If patient outcomes are superior for one group, this test would determine whether the outcome difference is associated with greater or lesser costs.

Primary Hypothesis 6: Counselors in the experimental condition will report satisfaction with the BH-CDS Program. At the end of the study, participating counselors were asked to complete a satisfaction survey, which included both open-ended questions and Likert-type rating scale questions. Due to the small number of counselors in the experimental and control groups, formal statistical significance testing was not conducted. Instead, these data were analyzed descriptively. Open-ended text were subject to qualitative thematic analysis.

Results

Counselor Participants. A total of 24 counselors at four outpatient substance abuse treatment facilities around the United States participated in the current study.

Client Participants. One hundred and ninety patients completed consent forms and completed baseline surveys. Of these, 140 participants were fully enrolled into the study (completed the PDE, counselors obtained recommendations from the BHCDS system, participants completed the baseline survey). Forty-seven participants were randomized into the control, TAU, condition and 93 were randomized into the experimental condition. Demographics were relatively similar across the experimental and control conditions.

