Primary Hypothesis 1: Clients in the experimental condition will have significantly greater matched evidenced-based and wraparound services than clients in the control condition. Results test indicated no significant difference for experimental and control groups.

Primary Hypothesis 2: Clients in the experimental condition will have greater engagement in treatment than clients in the control condition. T-tests indicated that the experimental and control groups did not differ with respect to treatment engagement.

Primary Hypothesis 3: Clients in the experimental condition will have less frequent use of substances than clients in the control condition. The mean number of relapses during the study period for the experimental group was not significantly different from the control group.

Primary Hypothesis 4: Clients in the experimental condition will have greater biopsychosocial functioning than clients in the control condition. Results for psychiatric status, medical status, alcohol use, family status, or drug use were not significant. Employment status results suggest that participants in the experimental, CDS, condition had significantly fewer legal problems than controls.

Primary Hypothesis 5: Clients in the experimental condition will have greater cost effectiveness than clients in the control condition. The CDS program did not yield significantly different costs effectiveness than the control group.

Primary Hypothesis 6: Counselors in the experimental condition will report satisfaction with the BH-CDS Program. Overall, counselors found it easy to complete the CDS program and reported that their clients' reaction was "neutral" or "positive" (no counselors reported a negative client reaction).

Counselors exposed to the tailored recommendations, reported that they were easy to understand, easy to integrate into the client's treatment plan, and useful for informing treatment decisions and were more likely to incorporate the tailored recommendations into future treatment planning.

Conclusion

Although the use of clinical decision support is promising, the present effort was unable to empirically demonstrate a direct impact on outcome, retention, amount of service delivered or cost. Further research on the impact of clinical decision support for substance use treatment is warranted.

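### Hypothesis 5 is posed and reported as cost-effectiveness, but the only analysis described compares mean service cost

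*SAP*

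**What the plan says.** Under Analyses by Hypothesis, Primary Hypothesis 5 is "Clients in the experimental condition will have greater cost effectiveness than clients in the control condition". Services found in the chart review are priced by CPT code at Massachusetts Medicare rates, and then "Costs per individual were summed and averaged for t-test comparison between experimental and control groups". Outcomes appear only in a closing conditional sentence: "If patient outcomes are superior for one group, this test would determine whether the outcome difference is associated with greater or lesser costs". No outcome measure is chosen for this hypothesis, and no ratio, net benefit or other joint estimate of cost and effect is described.

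Under Results, the line for Hypothesis 5 is "The CDS program did not yield significantly different costs effectiveness than the control group". It gives no arm means, difference, interval or p-value. The Conclusion is narrower: it says that the effort was "unable to empirically demonstrate a direct impact on outcome, retention, amount of service delivered or cost".

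The Primary Analytic Approach lists no cost question, so the Hypothesis 5 paragraph is the only definition of this analysis. That opening section does give the nesting of clients within counselors as one reason for choosing mixed models.

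**The concern.** A reader of the Results line would take it that cost-effectiveness was estimated, compared between arms and found not to differ. The described method supports only a statement about mean service cost.

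The conditional sentence has a related fault. It assigns to the cost t-test the task of determining whether an outcome difference is associated with cost. A two-arm comparison of cost has no outcome variable in it, so it cannot measure such an association. At most, a cost difference and an outcome difference can be set side by side.

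A secondary point is that the t-test as described treats clients as independent, although the SAP's own general approach says that counselor nesting should be accounted for.

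**Working it through.** The SAP gives no cost mean, SD, p-value or interval for Hypothesis 5, so there is no figure to reproduce. The check is a comparison of texts, plus an illustration of precision in SD units.

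**1. What each statement is about**

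| Place in the SAP | Quantity |
|---|---|
| Hypothesis 5, hypothesis sentence | cost-effectiveness |
| Hypothesis 5, method | mean CPT-priced service cost per client |
| Hypothesis 5, conditional sentence | association of an outcome difference with cost; outcome not named |
| Results, Hypothesis 5 | cost-effectiveness |
| Conclusion | cost |

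The method and the Conclusion agree with each other. The hypothesis and the Results line name something else.

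**2. Why the cost test cannot stand in for the hypothesis**

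Write ΔC for the difference in mean cost, ΔE for the difference in mean effect, and λ for the value of one unit of effect. Net benefit is λΔE − ΔC. The t-test uses only the cost data, so its statistic does not change when ΔE changes. For example, take ΔC = 0 and λ = 1000 (assumed, arbitrary units). Then ΔE = −0.1, 0 and 0.1 give net benefits of −100, 0 and 100. The same cost result is compatible with worse, equal or better cost-effectiveness.

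**3. How precise the cost comparison is**

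Inputs from the Results section: 47 control clients, 93 experimental clients (47 + 93 = 140) and 24 counselors. Assumed: all 140 have cost data, and the cost SD is equal in both arms.

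- Standard error in SD units: √(1/47 + 1/93) = 0.179.
- No clustering: t(0.975, 138 df) = 1.977; half-width 1.977 × 0.179 = 0.354 SD.
- Mean cluster size: 140/24 = 5.83. Design effect = 1 + (5.83 − 1) × ICC, where ICC is the intraclass correlation within counselor. It is 1.24 at ICC 0.05 and 1.48 at ICC 0.10. Both ICCs are assumed.
- With each counselor in one arm and equal cluster sizes, df = 24 − 2 = 22 and t(0.975) = 2.074. The half-width is 2.074 × 0.179 × √1.24 = 0.41 SD, or 2.074 × 0.179 × √1.48 = 0.45 SD.

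None of this can be put in dollars, because the SAP gives no cost SD.

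**The case against.** The strongest defence is that the method is fully disclosed, its costs are called imprecise, and the conditional sentence shows that cost was meant to be read beside separately tested outcomes. Hypotheses 1 to 3 are reported without a significant difference, as are five domains under Hypothesis 4 ("Results for psychiatric status, medical status, alcohol use, family status, or drug use were not significant"). On the authors' reading there was no superior outcome to set against cost, so a cost comparison was all that remained. This reduces the practical effect of the label. It does not make the Results line correct: non-significant outcomes are not equal outcomes, and cost-effectiveness was still not estimated.

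Four stronger readings are tempting, and the SAP does not support them.

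- *The cost test says nothing about cost-effectiveness.* Too strong: the cost difference is one component of net benefit. Power for a net-benefit test cannot be fixed either. With equal true costs, independent clients, an outcome difference of 0.3 to 0.5 SD and one outcome SD worth one to two cost SDs, all assumed, power runs from 16% to 89% as the cost-outcome correlation goes from −0.5 to 0.5. That range reflects the assumptions, not the trial.
- *Ignoring counselors inflated the type I error.* This holds if condition varies between counselors. The SAP says that participants were randomized but also speaks of counselors in both groups. If counselors had clients in both arms, the inflation shown does not apply. Hypotheses 2 and 3 also use plain t-tests, so the inconsistency is not peculiar to Hypothesis 5.
- *The outcome condition was met.* The one positive result reads "Employment status results suggest that participants in the experimental, CDS, condition had significantly fewer legal problems than controls". It opens on one domain and ends on another, so it cannot serve as the named outcome until it is reconciled.
- *The cost of the tool was left out of one arm.* No tool cost is stated, but full enrolment of all 140 clients is described as including that "counselors obtained recommendations from the BHCDS system". A difference between arms in tool cost cannot be determined.

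**Conclusion.** The point holds in this form. Hypothesis 5 was posed as cost-effectiveness, only service cost was compared, and the Results line reports a null on the untested quantity. The conditional sentence also claims more than a cost t-test can deliver. This rests on the text alone and on no assumed figure.

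The missing counselor term is a real inconsistency with the general approach, but it is secondary and its size is unknown. The half-widths of 0.35 SD and of 0.41 to 0.45 SD are illustrations under the stated assumptions. They serve only to show that non-significance should not be read as equal cost. The Conclusion does not share the fault.

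**What to change.** - Keep the Hypothesis 5 wording and the conditional sentence on record. The document already contains results, so rewriting or deleting them now would hide that the hypothesis as posed went untested.
- Add a dated note stating that cost-effectiveness was not tested and that the cost t-test cannot determine an association with outcome.
- Correct the Hypothesis 5 line in Results to say: no significant difference was found in mean CPT-priced service cost per client; cost-effectiveness was not tested.
- Report both arm means and the mean difference with a 95% confidence interval, from a model with a random counselor effect and small-sample degrees of freedom. State whether counselors had clients in one arm or both.
- Leave the Conclusion as it is.

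The cost is one note, one corrected line and a small re-analysis of data already in hand. The downside is a narrower statement for Hypothesis 5. No new clients or data are needed.

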Statistical Plan, Results and Conclusions for:

A Clinical Decision Support Tool for Electronic Health Records (Official Title)

NCT number 02697643

Document Date: August 9, 2018

Analytic Approach.

Primary Analytic Approach. We are interested in learning whether participants in the intervention condition, BH-CDS, as compared to the control condition, treatment as usual, have (1) greater access to wraparound services, (2) more treatment visits, and (3) longer retention in treatment. As secondary hypotheses, we will examine whether the intervention condition, as compared to the control condition, will be associated with significantly (1) greater psychosocial outcomes, and (2) reduced drug use. A mixed model analytic approach was chosen for its ability to: adjust for individual-level covariates; take into account nesting of clients within counselors; and efficiently maximize the correlated nature of the repeated measures data in the design. Each mixed model will include fixed effects (condition, time and condition-by-time); random effects (clients nested within counselors); repeated measures variation (time); as well as potential counselor-level demographic covariates (e.g., experience level) and client-level demographic covariates (i.e., age). Non-significant covariates will be removed systematically. After arriving at the final model for each analysis, the condition-by-time effect will be examined for significance. In the presence of a significant condition-by-time effect, Bonferroni corrected post-hoc contrasts will be conducted to test for differences between conditions on mean change from baseline to one month follow-up and baseline to three month follow up

Analyses by Hypothesis

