Primary Hypothesis 1: Clients in the experimental condition will have significantly greater matched evidenced-based and wraparound services than clients in the control condition. To address this hypothesis, a chart review was conducted to enumerate services received during the study period. The percentage of services that clients in the experimental condition received from the list of tailored recommendations was calculated. We then compared this percentage to the percentage of services that clients in the control condition would have received had they been in the experimental condition and received tailored recommendations. Because all clients participating in the study completed the PDE, we were able to determine which set of recommendations clients in the control condition would had received had they been in the experimental.

Primary Hypothesis 2: Clients in the experimental condition will have greater engagement in treatment than clients in the control condition. Engagement in treatment was calculated by dividing the number of treatment sessions attended during the study period by the total number of scheduled treatment sessions (i.e., opportunities for treatment), a sum of treatment sessions attended plus the number of scheduled sessions that the client did not show up for (no-show). An independent samples T-test was utilized to determine whether there were statistically significant differences between participants in the experimental and control groups with respect to treatment engagement.

Primary Hypothesis 3: Clients in the experimental condition will have less frequent use of substances than clients in the control condition. Use of substances was measured by the number of relapses during the study period. An independent samples *T*-test was conducted to evaluate whether participants number of relapses differed significantly between the experimental and control groups.

Primary Hypothesis 4: Clients in the experimental condition will have greater biopsychosocial functioning than clients in the control condition. Biopsychosocial functioning was captured by the seven ASI-MV composite scores. The ASI-MV was administered at baseline, 1-month follow-up and 3-month follow-up. Change in the ASI-MV composite scores was evaluated over time and across participant groups with a repeated measures mixed model.

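### Facility is in no described analysis, so differences among the four sites stay in the error term and any site-by-arm imbalance would go uncorrected

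*SAP*

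**What the plan says.** Under Results, Counselor Participants, the SAP reports that 24 counselors took part, at "four outpatient substance abuse treatment facilities around the United States". Under Client Participants it adds that "140 participants were fully enrolled into the study" and that "Forty-seven participants were randomized into the control, TAU, condition and 93 were randomized into the experimental condition". No count of arms by facility is given. Balance is described only by a remark that demographics were broadly alike.

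The Primary Analytic Approach lists the model terms: "Each mixed model will include fixed effects (condition, time and condition-by-time); random effects (clients nested within counselors); repeated measures variation (time", followed by "potential counselor-level demographic covariates (e.g., experience level) and client-level demographic covariates (i.e., age". Covariates that are not significant are then dropped. Facility is in neither list.

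Under Analyses by Hypothesis and the H5 paragraph, the methods are:

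- H1 (share of recommended services received): two percentages are compared, with no named test.
- H2 (sessions attended divided by sessions scheduled): "An independent samples T-test was utilized to determine" whether the arms differ.
- H3 (number of relapses): independent-samples t-test.
- H4 (seven ASI-MV composites at baseline, 1 and 3 months): repeated-measures mixed model.
- H5 (CPT-coded services priced from one Massachusetts Medicare list): t-test on cost per client.

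None of these mentions facility, as a covariate, stratum or random effect.

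**The concern.** The services a client can receive, the sessions that are scheduled and the volume of billable care plausibly depend on the facility. If so, part of the variation in H1, H2 and H5, and perhaps H3, is between sites. A two-group t-test leaves that variation in the error term. If one arm is over-represented at a site with richer services or better attendance, the t-test counts part of the site difference as a treatment difference.

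The SAP accepts clustering in principle, since it specifies "random effects (clients nested within counselors" as random effects, but it stops below the facility and omits even the counselor from the t-tests. A counselor random effect takes up some between-site variance. It assumes, however, that counselor effects are unrelated to condition, so it does not remove confounding of site with arm.

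The Conclusion rests on null findings for outcome, retention, services and cost, so avoidable noise in those comparisons matters.

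**Working it through.** **Inputs.** From the SAP: 4 facilities, 24 counselors, 47 control and 93 experimental clients (47 + 93 = 140, which agrees with the enrolled total; ratio 1.98). The SAP gives no power calculation, significance level or site ICC, so there is no planned figure to reproduce. Assumed here: two-sided 5% level, 80% power, four equal sites, and site ICC of 0.02, 0.05, 0.10 or 0.20.

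**Step 1. Precision, clients randomized individually.** The unadjusted minimum detectable difference (MDD) is (1.960 + 0.842) × √(1/47 + 1/93) = 2.802 × 0.1790 = 0.501 SD. With site in the model and arms nearly balanced within site, it is multiplied by √(1 − ICC). Power at 0.5 SD is Φ(0.5 / [0.1790 × √(1 − ICC)] − 1.960).

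| Site ICC (assumed) | MDD, SD | Power at 0.5 SD |
|---|---|---|
| unadjusted | 0.501 | 79.8% |
| 0.02 | 0.496 | 80.6% |
| 0.05 | 0.489 | 81.8% |
| 0.10 | 0.476 | 83.8% |
| 0.20 | 0.448 | 87.8% |

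Without stratification, chance imbalance takes back a little of this. The expected R² of arm on site is 3/139 = 0.022, which multiplies the variance by 139/136 = 1.022. The MDDs become 0.501 × √(1.022 × (1 − ICC)) = 0.502, 0.494, 0.481 and 0.453 SD. At ICC 0.02 the gain has gone.

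**Step 2. Precision, counselors assigned.** With 24 counselors and equal caseloads, the expected R² of arm on site is 3/23 = 0.13, and the variance multiplier is 23/20 = 1.15. The ratio of adjusted to unadjusted model-based standard error is √(1.15 × (1 − ICC)):

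- 1.06, 1.05, 1.02 and 0.96 at ICC 0.02, 0.05, 0.10 and 0.20
- 0.90 if site explained 30% of the variance

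So the reported standard error need not fall.

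**Step 3. Shift in the arm difference due to site.** Its SD is √(ICC × 4 × 0.25 × 0.75 × N/(N − 1) × (1/n₁ + 1/n₀)).

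- Clients randomized (N = 140; 93 and 47): √(0.0242 × ICC) = 0.02, 0.03, 0.05 and 0.07 SD.
- Counselors assigned (N = 24; 16 and 8 assumed): √(0.147 × ICC) = 0.05, 0.09, 0.12 and 0.17 SD.

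A simulation of 20,000 trials per setting agreed to two decimals.

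**Step 4. Type I error of the unadjusted t-test (same simulation, unstratified).**

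- Clients randomized: 4.9%, 5.2%, 4.9% and 5.0%, so nominal.
- Counselors assigned: 5.8%, 7.5%, 9.0% and 13.8%, from site variance alone.

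**Step 5. H4.** The planned test is condition-by-time, with contrasts on change from baseline. A facility main effect adds the same amount at every visit and largely cancels from change. Only facility-by-time can matter there, and the figures in Step 1 do not carry over.

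**The case against.** The strongest reply is that no harm is shown. The SAP gives no arm-by-facility counts, and the unit of assignment and any stratification may be set out in a protocol that is not at hand. It says that participants were randomized. If that was done client by client, the shift due to site is 0.02 to 0.07 SD and the t-test keeps its level. This stands. A reader might infer that 24 counselors over four sites make an uneven split likely, or that the reported results are distorted by it; the document supports neither. The counselor reading remains open because the H6 paragraph speaks of counselors as belonging to the two groups.

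A reader might also infer that adjustment would cut the standard error by 5%, 11% or 16%, that is √0.9, √0.8 and √0.7 for site shares of 10%, 20% and 30%. Those savings require site and arm to be nearly unrelated, so they cannot be combined with an argument from imbalance, and the range leaves out small site effects.

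The mechanism has limits too. H2 is a ratio, which removes much of the difference in session volume. H5 uses one price list, so sites can differ in cost only through the mix and volume of services.

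Finally, carrying the promised counselor effect into the t-test outcomes would absorb much of the site variance and, if counselors were assigned at random, repair most of the inflation in Step 4. That also stands. It does not adjust for imbalance between site and arm, which a fixed facility effect does.

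**Conclusion.** The omission is certain: facility is in no described analysis. Its effect is moderate and depends on assumptions.

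- With individually randomized clients the loss is precision: nothing or about one power point at site ICC 0.02, and up to 8 points (79.8% to 87.8%) at 0.20 when arms are balanced within site. Without stratification, type I error stays near 5% with or without adjustment.
- With assigned counselors the issue is validity. The plain t-test would run at about 6% to 14% over the same ICC range, and adjustment need not shrink the reported standard error.
- For H4 a facility main effect alone would change little.

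Actual imbalance by site is unknown, and nothing here shows that any reported result would change. This is a cheap and standard improvement to the analysis.

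**What to change.** - **H1, H2, H3 and H5:** replace the t-tests, and the unnamed comparison in H1, with a model containing condition, facility as a fixed effect and the counselor random effect that the Primary Analytic Approach already promises. Use a fixed effect because four levels are too few to estimate a facility variance reliably.
- **Retention:** keep facility whatever its p-value, exempt from the rule that drops non-significant covariates.
- **H4:** add facility and facility-by-time.
- **Reporting:** tabulate arm by facility, and state the unit of assignment and any stratification, so that readers can see which case in the working applies.

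The cost is 3 df for facility. That is negligible against 140 clients, but takes 24 − 2 = 22 down to 19 if counselors were assigned. In H4, facility-by-time over three visits uses a further 3 × 2 = 6. Because the document already reports results, the change is a re-analysis of existing data as well as new wording. It must be labelled post hoc and shown beside the reported analyses.

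### Does the definition of the 140 fully enrolled clients mean that control counselors obtained the tool's recommendations, or that assigned clients were left out?

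*SAP*

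**What the plan says.** The relevant text is in the SAP's Results, under Client Participants. It starts from those who consented: "One hundred and ninety patients completed consent forms and completed baseline surveys". The enrolled subset is then described in these terms: "140 participants were fully enrolled into the study (completed the PDE, counselors obtained recommendations from the BHCDS system"; the parenthesis ends with completion of the baseline survey. The next sentence gives the arms: "Forty-seven participants were randomized into the control, TAU, condition and 93 were randomized into the experimental condition".

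Three other places bear on who had the recommendations:

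- Primary Analytic Approach sets the BH-CDS condition against a control of treatment as usual.
- Primary Hypothesis 1 (Analyses by Hypothesis) scores control clients against a list they did not receive. It gives the basis as "Because all clients participating in the study completed the PDE", from which the analysts could determine "which set of recommendations clients in the control condition would had received had they been in the experimental" condition.
- The results for Primary Hypothesis 6 first describe counselors overall and then a subgroup: "Counselors exposed to the tailored recommendations, reported that they were easy to understand".

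No sentence names an analysis set. Primary Hypothesis 5 speaks only of "Costs of services provided to the participating clients in the experimental and control conditions", and Primary Hypothesis 1 likewise of participating clients.

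**The concern.** Obtaining recommendations from the tool is part of delivering the intervention. When that step is a condition for being counted, and the counted clients are exactly the two arms, two worries follow.

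The first is contamination. Read literally, the counselors of all 47 control clients obtained the recommendations. Control would then not be plain usual care, and the contrast behind Hypotheses 1 to 5 would be weakened. A null result from an ineffective tool and one from a contaminated control mean different things.

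The second is selection. If condition was fixed before the step, clients whose counselors did not use the tool may have been dropped after assignment. The experimental arm would then be selected on counselor uptake and the control arm would not. The wording under Primary Hypothesis 6, "Due to the small number of counselors in the experimental and control groups, formal statistical significance testing was not conducted", places counselors themselves in arms. This leaves open that a client's condition was settled early through the counselor.

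**Working it through.** **Counts.** All inputs are from Results, Client Participants.

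- Arms: 47 + 93 = 140, which reproduces the stated enrolled count. Randomized and fully enrolled clients are therefore equal in number.
- Control share: 47 / 140 = 33.6%. This is the part of the set for which the wording conflicts. It does not measure an error in any estimate.
- Not fully enrolled: 190 − 140 = 50, and 50 / 190 = 26.3%. All 190 had the baseline survey, so by the listed conditions these 50 lacked the PDE, the recommendation step, or both.
- Allocation: 93 / 47 = 1.98 to 1. No intended ratio is stated.

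**Could the counts reveal a loss after assignment?** Suppose, purely as an assumption, that all 190 had been assigned.

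| Assumed allocation | Assigned (control / experimental) | Lost from control | Lost from experimental |
|---|---|---|---|
| 1:1 | 95 / 95 | 95 − 47 = 48 (50.5%) | 95 − 93 = 2 (2.1%) |
| 1:2, rounded | 63 / 127 | 63 − 47 = 16 (25.4%) | 127 − 93 = 34 (26.8%) |

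An uptake condition that applied only to the experimental arm should show as excess loss in that arm. The first row shows the opposite and the second shows nearly equal loss. This does not prove the absence of selection, because the ratio is assumed and equal losses can still be selective. It does mean that the counts offer no support for the feared mechanism.

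**Possible readings of the step, set against the rest of the document.**

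1. *Counselors in both arms obtained and could use the recommendations.* This fits the parenthesis alone. It conflicts directly with Primary Hypothesis 1, and by implication with the usual-care control and with the subgroup of exposed counselors under Primary Hypothesis 6.
2. *The step refers to the experimental workflow only.* This fits those three places. It would require condition to be known before the step, which sits awkwardly with an account that places randomization after enrolment.
3. *Recommendations were generated for every client from the PDE and withheld in control.* This fits the order of the account, the equality of 140 and 47 + 93, and Primary Hypothesis 1, which needs a recommendation list for each client in both arms. Only the phrase about counselors obtaining them is then too broad for control.

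The third reading leaves the least unexplained, although the document does not state it.

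**The case for a change.** The strongest reply is that calling this loose wording does not settle it, because the readings differ in consequence. The first is contamination even if randomization came after enrolment. The second makes enrolment a criterion applied after assignment. Only the third is harmless, and it is nowhere written. Meanwhile 50 of 190 patients go without a reason, an arm or a time, and no analysis set is named.

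Part of this stands. The parenthesis does not distinguish arms, the order of the step and assignment is not stated outright, and a reader would be helped by one sentence on each.

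The rest does not carry. Against one compressed parenthesis stand three places that agree that control did not have the tool, so the question can be answered from the document as a whole. Exclusion after assignment is possible but not shown: the patients are described as consenting, then enrolling, then being randomized, and the totals match. The procedure and timing of randomization are commonly left to a protocol, which is not available here, so silence on them is not a fault of the SAP.

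The natural remedy would be a primary set of all assigned clients, with Hypothesis 1 limited to those with a completed PDE. That brings little. If none of the 50 was assigned, it returns the same 140 and the same results. If some were, it needs new chart abstraction and reruns of Hypotheses 1 to 5, all already reported. If PDE completion could follow assignment, limiting Hypothesis 1 to completers would also reintroduce the kind of conditioning that the remedy is meant to remove.

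**Conclusion.** No change to the plan follows. There is a genuine but minor inconsistency between the enrolment description under Client Participants and the hypothetical treatment of control recommendations under Primary Hypothesis 1. It concerns how 47 of 140 clients are described. No assigned client is shown to be missing, and neither the size nor the direction of any bias can be worked out from what is given.

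The conclusion rests on two assumptions: that the order of the account (190, then 140, then 47 and 93) is the order of events, and that the three places separating control from the tool describe the trial correctly. If records showed that some of the 50 had been assigned, the selection question would reopen. Nothing in the document shows this. A report could usefully say whether the step applied to the experimental arm only or recommendations were withheld in control, and whether randomization followed full enrolment. That is a matter of reporting and does not affect the analyses.
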